Study Product(s), Dose, Route, Regimen	
Arm A: Abemaciclib 200 mg orally BID Days 1-21
 
Arm C:

	
Atezolizumab 1200 mg IV on Day 1 OR Abemaciclib 200 mg orally BID Days 1-21
 
All cycles are 21 days in length. Starting doses are subject to safety analyses.

Duration of Administration	
Patients may be treated until disease progression or unacceptable toxicity or other reasons subject to Investigator/patient discretion.

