## 5. TREATMENT PLAN

### 5.1. Treatment Regimen

Protocol treatment must start within 7 calendar days of enrollment. All study therapy will be administered on an outpatient basis. Unless otherwise specified, treatment delay of more than 28 days from date of last intended therapy will result in treatment discontinuation. For combination therapy regimens, a new cycle will not start until atezolizumab and/or abemaciclib are given. No minimum time interval is required between abemaciclib and atezolizumab administration. Vomited should be skipped, and abemaciclib dosing resumed at the next scheduled dose. If a dose is missed, it may be taken when remembered if there are at least 6 hours before the next scheduled dose. Held doses of atezolizumab or abemaciclib will be considered omitted for that cycle.

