## 5.5 Duration of Follow Up

After treatment discontinuation, patients will be followed every 3 months for 24 months or until death, whichever occurs first. Participants removed from protocol therapy for unacceptable adverse event(s) will be followed until resolution or stabilization of the adverse event and for PSA and/or radiographic progression until a new treatment is started, the patient withdraws from study procedures, or death.

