**Table 27. Study Calendar**

Procedures	Screening 	Cycle 1 Day 1	Cycle 2 Day 1	Cycle 3 Day 1	Cycle 4+ Day 1	EOT 	Follow- Up 	EDC Timepoints
Informed Consent	X							NA
Physical Exam, Vital Signs, Weight 	X	X	X	X	X	X		Every cycle. Height only at screening
ECOG Performance Status	X	X	X	X	X	X		Screening, Every cycle, EOT
Toxicity Review 	X	X	X	X	X	X	X	Screening, Every cycle, EOT and Follow Up
Review of Concomitant Medications	X	X	X	X	X	X		Screening, Every cycle, EOT
CBC w/ Diff	X	X	X	X	X	X		Screening, Every cycle, EOT
Comprehensive Metabolic Panel	X	X	X	X	X	X		Screening, Every cycle, EOT
TSH, Free T4 		X	X 	X 	X	X		Cycle 1 day 1, Every cycle when collected, EOT
PSA	X	X	X	X	X	X	X	Screening, Every cycle, EOT and Follow up
Testosterone	X							Screening
Imaging & Response Assessment	X				X 		X	Screening, Every 3 cycles starting at C4D1, follow up
Tc  m Bone Scan	X				X 		X	Screening, Every 3 cycles starting at C4D1, follow up
PFTs	X 				X 			Screening and Cycle 4 Day 1
Research Blood	X 	X 		X 	X 	X 		C1D1, C3D1, C6D1, C9D1, C12D1, and EOT
Coagulation Blood Tests (PT/INR and aPTT)	X		X					
Archival Tumor Tissue	X 							Screening
On-treatment Tumor Biopsy				X 				Cycle 3 D1
Abemaciclib  (Dispensation, Diary Review & Reconciliation)		X	X	X	X	X		All cycles and EOT
Atezolizumab Administration 		X	X	X	X			All Cycles
Survival Status							X	Follow up

1. Baseline assessments must be completed within 21 days prior to registration.
2. Visit must be completed within 30 days of last dose of protocol therapy.
3. Survival follow-up every 3 months for 24 months post EOT visit  $\pm$  1 week. For subjects who discontinue treatment for reasons other than PD, scans should continue to be completed at regular intervals (approximately every 9 weeks or as per institutional standard), and PSA should continue to be measured at regular intervals (approximately every 3 weeks or as per institutional standard) until a new treatment is started, the patient withdraws from study procedures, or death.
4. Vital signs include temperature, pulse, respirations, blood pressure. Height will be obtained at screening only. Physical exam can be excluded when a virtual visit is required due to COVID-19 pandemic.

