5. Data on adverse events will be collected from the time of the initial study drug administration through 100 days after the last dose of study drug. Data will also be collected regarding any serious adverse event that occurs more than 100 days after the last dose of study drug(s) and is considered related to study drug.
6. Only required for patients receiving atezolizumab-containing regimens on cycle 1 day 1 and every 3 cycles, otherwise only as clinically indicated.
7. MRI or CT of abdomen and pelvis along with chest CT with or without IV contrast. Brain CT or MRI with (preferred) or without IV contrast as indicated. To be assessed every 3 cycles (-1 week window) beginning with C4D1, i.e. within 1 week of planned C4D1, C7D1, etc. If the initiation of cycle 4, cycle 7, etc. is planned to be delayed (for toxicity management, scheduling, or any other reason), then imaging should be delayed as well. However, if imaging studies are performed and intercurrent toxicities preclude initiation of C4D1, C7D1, etc. within 1 week, the imaging does not need to be repeated prior to eventual initiation of the next treatment cycle.
8. PFTs include spirometry, lung volumes and DLCO. If PFTs after 3 months of trial therapy do not meet criteria for grade 1 or higher pneumonitis/ILD, then further monitoring PFTs are not required. If a patient develops grade 1 or higher pneumonitis/ILD, PFTs should be obtained every 8 weeks until resolution; if a patient develops grade 2 or higher pneumonitis/ILD, they must be discontinued from trial therapy.
9. Research blood at time of screening is whole blood collected in EDTA tube to isolate buffy coat for germline DNA, at subsequent time points are 2  $\times$  10mL serum tubes for exosome analysis, and 1  $\times$  10mL Streck® tube for cfDNA analysis. Collect C1D1 prior to administration of protocol therapy and after completing 2 cycles of protocol therapy  $\pm$  14 days. Collection also at C6D1, C9D1, and C12D1  $\pm$  3 business days.
10. May be collected and submitted up to 30 days after progression and prior to any intervening treatment. If progression collection is within 14 days of prior correlative blood collection, these research samples do not need to be collected.
11. Refer to section 9.1 for specimen requirement details.
12. Required after completing 2 cycles of protocol therapy  $\pm$  7 days, for all patients. Refer to section 9.1 for specimen requirement details.

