## 11. MEASUREMENT OF EFFECT

### 11.1 Antitumor Effect

For the purposes of this study, participants should be re-evaluated for response every 3 cycles (+/- 7 days). In addition to a baseline scan, confirmatory scans should also be obtained not less than 4 weeks following initial documentation of objective response.

Response and progression will be evaluated in this study using Prostate Cancer Working Group 3 (PCWG3) modifications (81) (section 11.2) to the new international criteria proposed by the Response Evaluation Criteria in Solid Tumors (RECIST) guideline (version 1.1) [Eur J Ca 45:228-247, 2009]. Changes in the largest diameter (unidimensional measurement) of the tumor lesions and the shortest diameter in the case of malignant lymph nodes are used in the modified RECIST criteria. Response and progression of osseous disease by bone scintigraphy will be per PCWG3 criteria (81).

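### Tumour scans follow cycle starts and are deferred when a cycle is delayed, so calendar-time PFS and 6-month PFS depend partly on the pattern of delays, with no fixed direction of error for 6-month PFS

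*Combined protocol and SAP*

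**What the plan says.** **On treatment.** Table 27, footnote 7, sets imaging as follows: "To be assessed every 3 cycles (-1 week window) beginning with C4D1, i.e. within 1 week of planned C4D1, C7D1, etc". If the start of one of those cycles "is planned to be delayed (for toxicity management, scheduling, or any other reason), then imaging should be delayed as well". The footnote adds that a scan already done need not be repeated if toxicity then holds up the cycle. Section 11.1 also counts in cycles, but with another window: "participants should be re-evaluated for response every 3 cycles (+/- 7 days".

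**Cycles and delays.** The Synopsis states "All cycles are 21 days in length". Under section 5.1, unless otherwise specified, "treatment delay of more than 28 days from date of last intended therapy will result in treatment discontinuation"; no cumulative limit is given. The same section says "Held doses of atezolizumab or abemaciclib will be considered omitted for that cycle".

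**Off treatment.** For patients who stop for reasons other than progression, footnote 3 of Table 27 says "scans should continue to be completed at regular intervals (approximately every 9 weeks or as per institutional standard", and asks for PSA as well. Section 5.6 sends all patients who discontinue to the follow-up in section 10. Section 5.5, writing only of those who stop for adverse events, asks for follow-up "for PSA and/or radiographic progression until a new treatment is started".

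**Endpoint.** Section 11.1.6 measures PFS from the start of treatment to clinical, soft-tissue or bone-scan progression, or death; a PSA rise alone does not count. Section 13.2 estimates 6-month PFS by Kaplan-Meier with a 90% confidence interval. For Arm A it also counts patients against a null of 12% and an alternative of 34%. Neither section gives a rule for late or missed scans, for interval censoring, or for a scan window around six months.

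**The concern.** Radiographic progression is dated by a scan, so moving the scan moves the date. Two patients with the same tumour course can have different recorded PFS because one had a cycle postponed. The trial has no concurrent control to absorb this: Arm A and the abemaciclib cohort of Arm C are each judged against a fixed 12%. Delays are foreseeable, since section 6.2 expects diarrhoea in most abemaciclib patients and requires doses to be suspended for several toxicities. The trial is open-label, and the footnote covers any reason for delay, so sites also have some discretion over when a co-primary endpoint is measured.

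**Working it through.** The plan states no figure for the effect of scan timing, so there is none to reproduce.

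**Inputs from the documents.** Cycles of 21 days with a scan every three cycles, so blocks of 63 days and undelayed scans at days 63, 126 and 189. With the one-week early window the third scan falls at days 182-189. True 6-month PFS is 12% (null) or 34% (alternative). PFS is exponential, as section 13.2 assumes for Arm C and as is extended here to Arm A. Six months is 182.6 days.

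**Assumptions not in the documents.** The share q of three-cycle blocks delayed by 14 days is 0, 30% or 50%. The share f of events dated exactly (death or clinical progression) is 0 or 30%.

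**Formula.** If every event is dated at the next scan, a patient is recorded progression-free at a cut exactly when the true event comes after the last scan s on or before that cut. The recorded rate is therefore 0.12^(s/182.6), averaged over the delay patterns. A share f dated exactly gives f × 0.12^(cut/182.6) + (1 − f) × that average.

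**Last scan before the cut, true rate 12%, f = 0:**
- day 126: 0.12^(126/182.6) = 23.2%
- day 140: 19.7%
- day 154: 16.7%
- day 182: 12.1%
- day 189: 11.1%
- day 203: 9.5%

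**Cut at day 196** (admits an undelayed third scan), q = 30%. No block delayed, probability 0.7³ = 0.343, last scan day 189. Only the third block delayed, 0.147, day 126. One of the first two delayed, 0.42, day 140. Both of the first two delayed, 0.09, day 154. The sum is 0.343 × 11.1% + 0.147 × 23.2% + 0.42 × 19.7% + 0.09 × 16.7% = 17.0%. The other entries follow in the same way:

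| Cut | No delay | q = 30% | q = 50% |
|---|---|---|---|
| Strict six months, f = 0 | 23.2% | 21.1% | 19.8% |
| Day 196, f = 0 | 11.1% | 17.0% | 18.3% |
| Just past day 203, f = 0 | 11.1% | 12.0% | 14.0% |
| Day 196, f = 30% | 10.9% | 15.0% | 15.9% |

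Under the 34% alternative with f = 0, the day-196 rate goes from 33% to 40-42%, and the strict six-month rate from 48% down to 44-45%.

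**Recorded PFS time** (null, f = 0). The mean is E[block] / (1 − E[exp(−λ × block)]), with λ = −ln 0.12/182.6 = 0.0116 per day. It moves from 121 days to 124 (q = 30%) or 126 (q = 50%); the true mean is 86. Delays always lengthen it, but most of the excess over 86 comes from the 63-day interval itself.

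**Third scan at the landmark.** With no delay at all, a third scan at day 182 records 12.1% at a strict six months, while one at day 189 leaves day 126 as the last scan and records 23.2%.

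**Consequence for the Arm A count.** Taking the printed threshold of 6 of 27 at face value and ignoring stage 1, the binomial chance of reaching it at a true 12% depends on the recorded rate: 0.10 at 12.1%, 0.29 at 16.7%, 0.45 at 19.7% and 0.62 at 23.2%.

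**The case against.** The strongest reply is that the size, and even the sign, depend on the cut. The day-196 cut admits an undelayed third scan at day 189 and excludes one delayed to day 203, which produces the largest rise. At a strict six months, the closest reading of the Kaplan-Meier plan, delays bring the recorded rate nearer to the true 12%, and a fixed calendar with a third scan at day 189 has the larger error. That stands. It means that scan drift and the six-month landmark must be repaired together; it does not make the drift acceptable.

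The inputs are also assumed. No delay frequency is given, and held doses count as omitted, so not every hold postpones a cycle. Deaths and clinical progression are not tied to scans. These points limit the size but leave the mechanism.

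Three stronger readings are tempting, and the documents do not support them:
- A reader might infer that delays inflate 6-month PFS and favour the drug. The table shows both directions, and the scan schedule behind the historical 12% is not given, so the net bias against that benchmark cannot be determined.
- A reader might infer that patients off treatment may be followed by PSA alone. Footnote 3 asks for scans and PSA after any stop without progression, and section 5.6 points all who discontinue to section 10. Section 5.5 is a mismatch to reconcile.
- A reader might infer that deferred scans weaken pulmonary surveillance. The statement about chest CT at each tumour assessment is in the atezolizumab guidance of section 6.1, and section 6.2 gives pulmonary symptoms their own work-up.

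**Conclusion.** The point holds in a bounded form. As written, the plan lets tolerability and scheduling help to set radiographic progression dates, and nothing in sections 11.1.6 or 13.2 offsets this. Recorded PFS times move later, by about 3 to 5 days in the mean under the illustrated delays. Recorded 6-month PFS for a true 12% can move by up to about 7 percentage points upward or 3 downward, depending on the cut. The upward shift is about 5 points if 30% of events are dated exactly. These figures rest on exponential PFS, 14-day delays and an assumed 30-50% of blocks delayed. They illustrate sensitivity and do not predict the trial's bias.

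The drift cannot be judged apart from the landmark: an undelayed third scan already straddles six months, and that alone can move the recorded rate between 12% and 23%. The change is worth making because it costs little and protects a co-primary endpoint.

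**What to change.** 1. In Table 27, footnote 7, and section 11.1, schedule imaging every 9 weeks from cycle 1 day 1 with one common window, regardless of dose delays. Delete the rule that imaging is deferred with the cycle.
2. Require the third scan on or before the six-month landmark (a scan at day 182 records about 12% for a true 12%), or add an interval-censored sensitivity analysis to section 13.2. Step 1 alone leaves about 23% recorded for a true 12% if the third scan is at day 189 and all events are dated at scans.
3. In footnote 3, keep the same 9-week calendar for patients who stop without progression and remove the institutional-standard alternative.
4. Reconcile section 5.5 with footnote 3 and section 5.6, so that radiographic follow-up is stated alike for all who stop without progression.

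The cost is protocol wording, and at most a one-week shift of the third scan. In delayed patients the scan may no longer fall in the week before the next cycle.

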## 11. MEASUREMENT OF EFFECT

### 11.1 Antitumor Effect

For the purposes of this study, participants should be re-evaluated for response every 3 cycles (+/- 7 days). In addition to a baseline scan, confirmatory scans should also be obtained not less than 4 weeks following initial documentation of objective response.

Response and progression will be evaluated in this study using Prostate Cancer Working Group 3 (PCWG3) modifications (81) (section 11.2) to the new international criteria proposed by the Response Evaluation Criteria in Solid Tumors (RECIST) guideline (version 1.1) [Eur J Ca 45:228-247, 2009]. Changes in the largest diameter (unidimensional measurement) of the tumor lesions and the shortest diameter in the case of malignant lymph nodes are used in the modified RECIST criteria. Response and progression of osseous disease by bone scintigraphy will be per PCWG3 criteria (81).

#### 11.1.1 Definitions

Evaluable for Target Disease response. Only those participants who have measurable disease present at baseline, have received at least one cycle of therapy, and have had their disease re-evaluated will be considered evaluable for target disease response. These participants will have their response classified according to the definitions stated below. (Note: Participants who exhibit objective disease progression prior to the end of cycle 1 will also be considered evaluable.)

Evaluable Non-Target Disease Response. Participants who have lesions present at baseline that are evaluable but do not meet the definitions of measurable disease, have received at least one cycle of therapy, and have had their disease re-evaluated will be considered evaluable for non-target disease. The response assessment is based on the presence, absence, or unequivocal progression of the lesions.

#### 11.1.2 Disease Parameters

Measurable disease. Measurable lesions are defined as those that can be accurately measured in at least one dimension (longest diameter in the plane of measurement is to be recorded) with a minimum size of:

- 10mm by CT scan (irrespective of scanner type) for studies with a slice thickness of  $\leq 5$ mm or twice the slice thickness or MRI
- 10mm caliper measurement by clinical exam (lesions which cannot be accurately measured with calipers should be record as non-measurable)
- 20mm by chest X-ray (if clearly defined and surrounded by aerated lung)

All tumor measurements must be recorded in millimeters (or decimal fractions of centimeters).

Malignant lymph nodes: To be considered pathologically enlarged and measurable, a

lymph node must be  $\geq 15$  mm in short axis when assessed by CT scan (CT scan slice thickness recommended to be no greater than 5 mm). At baseline and in follow-up, only the short axis will be measured and followed.

Note: Tumor lesions that are situated in a previously irradiated area will only be considered measurable if they have had subsequent progression by at least 5mm.

Non-measurable disease. All other lesions (or sites of disease), including small lesions (longest diameter  $< 10$  mm or pathological lymph nodes with  $\geq 10$  to  $< 15$  mm short axis), are considered non-measurable disease. Bone lesions without measurable soft tissue component, leptomeningeal disease, ascites, pleural/pericardial effusions, lymphangitis cutis/pulmonis, inflammatory breast disease, abdominal masses (not followed by CT or MRI), and cystic lesions are all non-measurable.

Target lesions. All measurable lesions up to a maximum of 5 lesions per organ and 10 lesions in total should be identified as target lesions and recorded and measured at baseline. Target lesions should be selected on the basis of their size (lesions with the longest diameter), be representative of all involved organ(s), but in addition should be those that lend themselves to reproducible repeated measurements. If a non-nodal lesion is either not present or is initially measured with longest diameter  $< 10$  mm as a non-target then grows to  $> 10$  mm after baseline, this lesion is assessed as a new target lesion as per iRECIST criteria (80). Per iRECIST, new lesions are assessed as per RECIST 1.1 but are recorded separately on the case report form (but not included in the sum of lesions for target lesions identified at baseline).

Lymph nodes merit special mention since they are normal anatomical structures which may be visible by imaging even if not involved by tumor. Pathological nodes which are defined as measurable and may be identified as target lesions must meet the criterion of a short axis of  $\geq 15$  mm by CT scan. Only the short axis of these nodes will contribute to the baseline sum. The short axis of the node is the diameter normally used by radiologists to judge if a node is involved by solid tumor. Nodal size is normally reported as two dimensions in the plane in which the image is obtained (for CT scan this is almost always the axial plane; for MRI the plane of acquisition may be axial, sagittal or coronal). The smaller of these measures is the short axis. For example, an abdominal node which is reported as being 15 mm x 30 mm has a short axis of 15 mm and qualifies as a malignant, measurable node. In this example, 15 mm should be recorded as the node measurement. All other pathological nodes (those with short axis  $\geq 10$  mm but  $< 15$  mm) should be considered non-target lesions. Nodes that have a short axis  $< 10$  mm are considered non-pathological and should not be recorded or followed.

A sum of the diameters (longest for non-nodal lesions, short axis for nodal lesions) for all target lesions will be calculated and reported as the baseline sum diameters. If lymph nodes are to be included in the sum, then as noted above, only the short axis is added into the sum. The baseline sum diameters will be used as reference to further characterize any objective tumor regression in the measurable dimension of the disease. If a non-target

lymph node grows to  $>15$  mm after baseline, this node is assessed as a new target lesion as per iRECIST. Per iRECIST, new lesions are assessed as per RECIST 1.1 but are recorded separately on the case report form (but not included in the sum of lesions for target lesions identified at baseline).

Non-target lesions. All other lesions (or sites of disease) including pathological lymph nodes should be identified as non-target lesions and should also be recorded at baseline. Measurements are not required and these lesions should be followed as ‘present’, ‘absent’, or in rare cases ‘unequivocal progression’ (more details to follow). In addition, it is possible to record multiple non-target lesions involving the same organ as a single item on the case record form (e.g., ‘multiple enlarged pelvic lymph nodes’ or ‘multiple liver metastases’).

#### 11.1.3 Methods for Evaluation of Disease

All measurements should be taken and recorded in metric notation using a ruler, calipers, or a digital measurement tool. All baseline evaluations should be performed as closely as possible to the beginning of treatment and never more than 4 weeks before the beginning of the treatment.

The same method of assessment and the same technique should be used to characterize each identified and reported lesion at baseline and during follow-up. Imaging-based evaluation is preferred to evaluation by clinical examination unless the lesion(s) being followed cannot be imaged but are assessable by clinical exam.

Clinical lesions. Clinical lesions will only be considered measurable when they are superficial (e.g., skin nodules and palpable lymph nodes) and  $\geq 10$  mm in diameter as assessed using calipers (e.g., skin nodules). In the case of skin lesions, documentation by color photography, including a ruler to estimate the size of the lesion, is recommended.

Chest x-ray. Lesions on chest x-ray are acceptable as measurable lesions when they are clearly defined and surrounded by aerated lung; however, CT is preferable.

Conventional CT and MRI. This guideline has defined measurability of lesions on CT scan based on the assumption that CT thickness is 5mm or less. If CT scans have slice thickness greater than 5 mm, the minimum size of a measurable lesion should be twice the slice thickness. MRI is also acceptable in certain situations (e.g. for body scans).

Use of MRI remains a complex issue. MRI has excellent contrast, spatial, and temporal resolution; however, there are many image acquisition variables involved in MRI, which greatly impact image quality, lesion conspicuity, and measurement. Furthermore, the availability of MRI is variable globally. As with CT, if an MRI is performed, the technical specifications of the scanning sequences used should be optimized for the evaluation of the type and site of disease. Furthermore, as with CT, the modality used at follow-up should be the same as was used at baseline and the lesions should be

measured/assessed on the same pulse sequence. It is beyond the scope of the RECIST guidelines to prescribe specific MRI pulse sequence parameters for all scanners, body parts, and diseases. Ideally, the same type of scanner should be used and the image acquisition protocol should be followed as closely as possible to prior scans. Body scans should be performed with breath-hold scanning techniques, if possible.

Ultrasound. Ultrasound is not useful in assessment of lesion size and should not be used as a method of measurement. Ultrasound examinations cannot be reproduced in their entirety for independent review at a later date and, because they are operator dependent, it cannot be guaranteed that the same technique and measurements will be taken from one assessment to the next. If new lesions are identified by ultrasound in the course of the study, confirmation by CT or MRI is advised. If there is concern about radiation exposure from CT, MRI may be used instead of CT in selected instances.

Endoscopy, Laparoscopy. The utilization of these techniques for objective tumor evaluation is not advised. However, such techniques may be useful to confirm complete pathological response when biopsies are obtained or to determine relapse in trials where recurrence following complete response (CR) or surgical resection is an endpoint.

PSA response and progression.

PSA response is defined per section 11.1.7, and PSA progression is defined per section 11.1.8.

Cytology, Histology. These techniques can be used to differentiate between partial responses (PR) and complete responses (CR) in rare cases (e.g., residual lesions in tumor types, such as germ cell tumors, where known residual benign tumors can remain).

The cytological confirmation of the neoplastic origin of any effusion that appears or worsens during treatment when the measurable tumor has met criteria for response or stable disease is mandatory to differentiate between response or stable disease (an effusion may be a side effect of the treatment) and progressive disease.

